10.2 Randomization and Stratification

Participants will be stratified by site (UVA, AHN). Randomization will occur with equal allocation to each ordering (Arm A or Arm B) using a stratified block randomization scheme with varying block sizes (of 2-4). Randomization will occur prior to the 2nd fraction of brachytherapy.

Version Date: 11/16/2021

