4 STUDY DESIGN

4.1 Overall Design

This is a two-center, stratified and randomized, four period, two arm crossover, non-inferiority trial to demonstrate that BrachyGel Vaginal Hydrogel Packing System is non-inferior to standard method vaginal packing (standard).

Two sites are included in the trial design in order to reflect the most common applicators used in intracavitary cervical cancer brachytherapy:

- Tandem and ovoid brachytherapy+/- interstitial needles (UVA cohort)
- Tandem and ring-based brachytherapy +/- interstitial needles (AHN cohort)

The BrachyGel Hydrogel Vaginal Packing System will be compared to gauze packing and/or rectal retractor packing per the institution's standard of care packing practice.

Participants will be stratified by site (UVA/AHN) and randomized to either Arm A or Arm B. Fraction 1 for all participants (both Arms) will be according to standard of care packing and fractions 2-5 (periods 1-4) will alternate between standard of care and BrachyGel packing, as shown in *Figure 1*.

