10.3.2 Study Outcomes & Endpoints

Study measurements will be captured post each fraction of treatment. Assessments may include:

- Adverse events
- Dosimetry
- Physicist evaluation of imaging/packing
- Physician evaluation of imaging/packing
- Participant discomfort survey

There are two primary endpoints based upon dosimetry measurements in the bladder and the rectum. Each endpoint is the difference between D2cc dosimetry measurements obtained during periods 1 and 2 (fractions 2 and 3 under the 2x2 crossover structure). Additional assessments include data from periods 3 and 4 (fractions 4 and 5).

Additional endpoints include measurements over all periods for:

- Bladder and rectal dosimetry as measured by D0.1 cc and D1 cc.
- Participant reported discomfort
- Physicist evaluated imaging properties
- Physician evaluated imaging properties
- Physician evaluated use experience

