10.4 Sample Size and Accrual

For this crossover study the primary comparison is based upon the 2x2 initial crossover portion. The primary endpoint is the difference of D2cc dosimetry measurements between periods 1 and 2 (fractions 2 and 3) for sequence arm A and sequence arm B based upon a two-sample comparison of the mean difference to the non-inferiority margin. Data from 51 patients treated at UVA with fraction 2 and 3 information, reported overall in Romano et al 2018¹⁹, with standard packing resulted in a mean (standard deviation) of 0.12 (1.56) and 0.10 (0.92) D2cc for the difference for bladder and rectal dosimetry, respectively. The

width of the 95% CI for the mean difference was 0.9 and 0.5 for bladder and rectal dosimetry, respectively. Based upon these measurements and clinical judgement, a non-inferiority margin of δ =(0.12+1.56=1.68) was chosen for this study.

Version Date: 11/16/2021

Justification for the sample size is based upon obtaining sufficient accrual to test the primary hypothesis that use of the hydrogel vaginal packing is non-inferior to standard packing methods in 1) bladder and 2) rectal dosimetry by more than a non-inferiority margin. Let $diff_A$ and $diff_B$ denote the differences between fractions.

The primary hypothesis to be tested is H_o : μ_{diffA} - μ_{diffB} $\geq \delta$ versus H_a : μ_{diffA} - μ_{diffB} $< \delta$, where the non-inferiority margin, δ =1.68, *each* for bladder and rectal, with a one-sided 2.5% level t-test. A sample size of 20 evaluable cervical cancer participants per arm achieves 94% power to detect non-inferiority using a one-sided t-test when the margin of non-inferiority is 1.68, the true difference between the means and the reference (standard) value is 0.12, and the assume population standard deviation is 1.56. Power is 96% if one uses the estimates for rectal dosimetry.

Adjusting for participants not satisfying the evaluable criteria (*section 10.3.1*), it is estimated that approximately 57 cervical cancer participants will need to be accrued to the study in order to test the primary study hypothesis. Each site may allow up to 10 oncologist and 4 physicists/dosimetrist to participate in completing the Physician and Physicist Assessments.

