10.6 Analyses

Two main sets of analyses for all endpoints are proposed. The first limits assessment to data from periods 1 and 2, and the second uses data from all periods. The first set will summarize data based upon differences between period endpoints, with comparisons by arm. The second will employ repeated measure models to estimate period effects.

For fractions 2-5, adverse events will be summarized by frequency and severity and packing type. For the ordinal measures, mean differences and 95% confidence intervals for the difference will be calculated by packing type. Repeated measure models will be used to describe treatment' effects over time and F-tests will be used to assess period affects. Graphical methods will aid in assessing model assumptions.

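### The primary t-test leaves out the site stratum used in the randomisation: a small, conservative loss of bladder power that a site term would recover, plus an unplanned by-site estimate

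*Combined protocol and SAP*

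**What the plan says.** Section 10.2 names site as the stratification factor ("Participants will be stratified by site (UVA, AHN") and describes the allocation: "Randomization will occur with equal allocation to each ordering (Arm A or Arm B) using a stratified block randomization scheme".

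Section 10.3.2 defines the two primary endpoints, bladder and rectum, within the participant: "Each endpoint is the difference between D2cc dosimetry measurements obtained during periods 1 and 2".

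Section 10.4 gives the primary test as "based upon a two-sample comparison of the mean difference to the non-inferiority margin", carried out for each organ "with a one-sided 2.5% level t-test". Section 10.6 describes the period 1-2 analysis in the same terms: "The first set will summarize data based upon differences between period endpoints, with comparisons by arm". The repeated-measures models in 10.6 are described without a site term, and no by-site summary is planned.

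Section 4.1 explains that the two sites were chosen to cover the common applicators. UVA uses tandem and ovoid; the other cohort is "Tandem and ring-based brachytherapy +/- interstitial needles (AHN cohort". The comparator is gauze and/or rectal retractor, whichever is each institution's standard.

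**The concern.** When allocation is balanced within strata, the stratum difference drops out of the treatment estimate. A test that ignores the strata still counts that difference as residual noise, so its standard error is too large and power is lost.

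Here the strata are not arbitrary. Site goes with the applicator and with the local standard packing. The planning mean and SD come from UVA patients alone, so they say nothing about the second site. The packing effect could also differ between applicators, and a single pooled estimate would not show it, although covering both applicators is the stated reason for having two sites.

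**Working it through.** **Inputs (10.4, bladder).** 20 evaluable per arm, margin 1.68, true difference 0.12, SD 1.56, one-sided 2.5%. For rectum the SD is 0.92 and the mean 0.10. The SDs come from 51 UVA patients, so they are within-site SDs. Assumed, because the documents give neither: two equal sites (10 per arm per site) and a gap D between the sites in the mean fraction 2-to-3 change.

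**1. The plan's own figures.** The UVA interval width reproduces: 2 × 2.009 × 1.56/√51 = 0.88, stated as 0.9. The power does not. SE = 1.56 × √(2/20) = 0.493, noncentrality = (1.68 − 0.12)/0.493 = 3.16, df = 38, which gives 0.869 against the stated 94%. A true difference of −0.12 would give 0.945. That discrepancy is a separate point; 0.869 is the baseline here.

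**2. Site level of D2cc.** A constant added to both fractions of every participant at one site cancels in the difference. In simulation (20,000 trials), a 2 Gy site gap in level left the SE at 0.490 and power at about 0.867, with or without a site term.

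**3. Site gap D in the fraction 2-to-3 change.** Because allocation is balanced within site, the arm contrast keeps its true SE of 0.493. Only the estimated variance is inflated, on average to about 1.56² + D²/4:

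- D = 0.5: +0.0625/2.4336 = +2.6%, SE 0.500
- D = 1.0: +0.25/2.4336 = +10%, SE 0.518
- D = 1.5: +0.5625/2.4336 = +23%, SE 0.547

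Putting the inflated SD straight into a power formula (0.861, 0.835, 0.793) overstates the loss, because it treats the estimate itself as noisier. The residual sum of squares divided by σ² is noncentral chi-square W on 38 df with noncentrality 4 × 10 × (D/2)²/σ² = 10D²/σ², independent of the arm contrast. The rejection probability is therefore the average over W of Φ[(margin − true)/0.493 − 2.024 × √(W/38)]. For type I error, set the true difference equal to the margin.

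| D (Gy) | Bladder power, no site term | Type I error, no site term | Bladder power, site term (37 df) |
|---|---|---|---|
| 0 | 0.869 | 0.025 | 0.868 |
| 0.5 | 0.863 | 0.024 | 0.868 |
| 1.0 | 0.845 | 0.020 | 0.868 |
| 1.5 | 0.814 | 0.015 | 0.868 |

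Simulation agrees: power without a site term was 0.862, 0.843 and 0.811 at the three gaps, and type I error at 1.0 and 1.5 Gy was 0.020 and 0.015, against 0.025 with the site term.

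**4. Rectum.** The same formula with SD 0.92 and true difference 0.10 gives power of at least 0.996 at every gap.

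**5. Site gap in the packing effect.** In this crossover that is a site-by-arm interaction. With a 1 Gy gap the simulated SE was 0.515 without a site term and 0.516 with it, so a site main effect recovers nothing.

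**6. Cost of the term when D = 0.** The t critical value moves from 2.024 to 2.026 and power from 0.8690 to 0.8685.

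**The case against.** The strongest reply is that the crossover has already done the work. Applicator and local packing most obviously affect the level of D2cc, and the level cancels. A reader might infer from the mismatch with the randomisation that the standard error carries between-site variation in general. Step 2 shows that it does not.

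Nothing in the documents points to a large gap in the fraction 2-to-3 change either. UVA's bladder change under standard packing is 0.12 with a 95% interval of about −0.3 to 0.6. Against 0.12, a gap of 1.0 to 1.5 Gy needs the second site to change by about 1.1 to 1.6 Gy, or by −0.9 to −1.4 Gy, between consecutive fractions. With no data from that site this cannot be excluded, but 0.5 Gy is easier to believe, and there the loss is under one power point. An unequal site split makes the inflation smaller still.

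All of this stands, and it sets the size of the point. It does not remove it. The site term costs almost nothing when there is no gap, and naming it in advance prevents a later choice between adjusted and unadjusted results. The reply also leaves untouched the lack of any by-site estimate.

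**Conclusion.** The primary test omits the stratification factor. The consequence is minor and runs in the conservative direction: bladder power falls by about 0.5, 2 and 5 points at assumed site gaps of 0.5, 1.0 and 1.5 Gy in the fraction 2-to-3 change, with practically no effect for rectum. These figures rest on equal sites, 10 per arm per site, the planning SD holding at both sites, and the 1.68 margin.

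Two stronger readings are tempting, and the documents support neither. A reader might infer that the omission endangers the non-inferiority conclusion; in fact type I error falls below 2.5%, so the omission cannot by itself produce a false claim. A reader might also infer that a site term would deal with different packing effects at the two sites; it does not, and only a by-site estimate shows them.

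The omission is certain from the text. The size of the loss is conditional on the assumed gap. The unreproduced 94% power and the conflict between the 1 Gy margin in 10.1 and the 1.68 in 10.4 are separate and larger matters.

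**What to change.** - In 10.4 and 10.6, test each organ with a linear model of the fraction 2-3 D2cc difference on arm and site. Compare the one-sided 97.5% confidence limit for the packing effect (the arm term, with the sign and scale on which the margin is stated) with the margin.
- Include site in the four-period repeated-measures model.
- Report the packing effect by site, with confidence intervals, as a supportive result labelled descriptive. With 10 per arm per site and SD 1.56, the 95% half-width for the bladder arm contrast is about 2.101 × 1.56 × √(2/10) = 1.47 Gy, too wide for a non-inferiority conclusion at either site alone.

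The cost is wording and one degree of freedom. No extra participants or data are needed: site is known at randomisation, and the physicist form in 13.2 already records the applicator.

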6.4 Registration and Randomization

All participants must sign the consent form prior to determination of eligibility for this study.

When a site is ready to enroll a patient, the following documentation must be scanned and emailed to the UVA Coordinating Center:

- Patient and staff signed signature page of the current informed consent form (ICF)
- Completed Inclusion/Exclusion checklist demonstrating subject eligibility
- Supporting documentation needed to confirm eligibility (lab results, scan results etc.)

Consult the Study Reference Manual for instructions on sending this information. The Coordinating Center will consult with the Overall Study PI if questions arise in confirming eligibility. The UVA Coordinating Center will communicate the subject number and arm assignment to the enrolling site.

Registration will occur following verification of eligibility by the treating physician. Eligibility confirmation and registration can occur after the 1st brachytherapy fraction but must occur before the 2nd brachytherapy fraction.

Participants who are consented and accrued to the study should be registered in the designated EDC System in accordance with the Clinical Trial Management System Policy. General guidelines are available in the User Manual and Data Entry Guide.

Participants should receive their first fraction of brachytherapy within 14 days of registration.

Randomization will be discussed with participants during the process of informed consent, and informed consent must be documented prior to randomization. Randomization will be stratified by institution, and will be based on equal allocation between arms. The randomization sequences will be generated by the study statisticians and loaded into RAND and accessed in the designated EDC System. Randomization will occur no sooner than 10 days prior to the second fraction of brachytherapy.

This study does not involve any blinding or masking procedures. Participants will be told which arm they are assigned to.

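### Printed block sizes of 2-4 make assignment at an open-label site about 72% guessable; larger undisclosed blocks are a cheap, minor improvement

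*Combined protocol and SAP*

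**What the plan says.** Section 10.2 sets the scheme. The two sites are the only strata, the two packing orders get equal shares, and the list follows a "stratified block randomization scheme with varying block sizes (of 2-4").

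Section 6.4 governs how assignments are made and seen:
- The list is central: "The randomization sequences will be generated by the study statisticians and loaded into RAND and accessed in the designated EDC System".
- Nothing is hidden afterwards: "This study does not involve any blinding or masking procedures. Participants will be told which arm they are assigned to".
- The site learns every result: "The UVA Coordinating Center will communicate the subject number and arm assignment to the enrolling site".
- Entry may come late: "Eligibility confirmation and registration can occur after the 1st brachytherapy fraction but must occur before the 2nd brachytherapy fraction". Section 10.1 makes fraction 1 the baseline dosimetry, so staff may already have seen it when they register a participant.

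Section 11.1.2 lets physicians and physicists who complete the surveys review the protocol. No section says that block sizes are kept from the sites.

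**The concern.** A central list conceals the file but not a pattern that can be worked out from earlier assignments. In an open-label trial stratified by site, staff can know every previous assignment at their site. With blocks of at most 4, one arm two ahead means that the next two assignments are fixed. With one arm one ahead, the other arm is the better guess.

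The stake is who enters, and when. Staff who expect a given order next could register a participant sooner or later, or not at all. The primary hypothesis in section 10.4 compares the mean fraction 2-3 difference between Arms A and B. It therefore relies on the two arms having the same expected change apart from packing. Steering on that expected change, or on who will complete the 3 fractions that section 10.3.1 requires, could enter the contrast.

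**Working it through.** The plan states no predictability figure, so there is none to reproduce.

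**Inputs.** From section 10.2: 1:1 allocation, two site strata, block sizes 2-4. From section 10.4: 57 to be accrued, 20 evaluable per arm, bladder SD of the difference 1.56, one-sided 2.5% test. The documents do not give the mix of sizes; I take 2 and 4 as equally likely per block and show the range.

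**1. Usable sizes.** A block of 3 cannot be split equally between two arms, which leaves 2 and 4.

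**2. Correct guesses.** The rule is to guess the arm that is behind at the site and toss a coin when the arms are level. It needs only the site's running count.
- Block of 2: (1/2 + 1)/2 = 1.5/2 = 75.0%.
- Block of 4: (1/2 + 2/3 + 2/3 + 1)/4 = 2.833/4 = 70.8%.
- Equal mix: (1.5 + 2.833)/(2 + 4) = 72.2%.

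Any mix lies between 70.8% and 75.0%; unrestricted randomization gives 50%. Simulating 57 participants, in one stratum or split 28/29 or 40/17, gives 71.7-71.8%.

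**3. Certain assignments.** A block of 4 opens with two of the same arm in 1/3 of cases, which fixes its last two places: 2 × 1/3 = 0.667 per block of 4.
- Equal mix: 0.667/6 = 11.1% in the long run.
- Range: 0% if all blocks are 2, and 0.667/4 = 16.7% if all are 4.

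Simulating 28 participants at a site, with a guesser who knows the sizes and past assignments, gives 72.0% correct and 10.4% certain. The second figure is slightly below 11.1% because a list of 28 can stop inside a block.

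**4. Effect on the primary test.** Suppose that staff steer every entry, so that participants differ by ±γ in expected fraction 2-3 change according to the guess. With g the proportion guessed correctly, each arm's mean moves by γ(2g − 1) in opposite directions, so the contrast shifts by 2γ(2g − 1).
- SE of the contrast: 1.56 × √(2/20) = 0.493 Gy.
- γ = 0.05 SD = 0.078 Gy, g = 0.72: shift = 2 × 0.078 × 0.44 = 0.069 Gy, or 0.069/0.493 = 0.14 SE. On a non-central t with 38 df, false non-inferiority is 3.4% instead of 2.5%.
- γ = 0.10 SD: shift 0.137 Gy, false non-inferiority 4.6%.

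These error rates depend on the shift in SE units, so they do not depend on the size of the non-inferiority margin. The values of γ are assumptions; the documents give none.

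**5. Alternatives (28 per site, guesser knows the rule).**

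| Scheme | Correct | Certain |
|---|---|---|
| Blocks 2/4 | 72.0% | 10.4% |
| Blocks 4/6/8 | 67.4% | 2.4% |
| Imbalance capped at 3 (big stick) | 57.5% | 15.0% |

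For 4/6/8, the running-count rule gives 68.1% in the long run.

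**The case against.** The case against making much of this is strong, and most of it stands.

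- **Arm is only order.** Every participant is planned to receive both packings, and the endpoint is a difference within the participant. Fraction 1 dosimetry shows a participant's D2cc level, which cancels. Nothing in the documents suggests that it predicts the change from fraction 2 to fraction 3.
- **The opportunity is narrow.** About 57 participants in 14 months at two sites is 57/14/2, or about 2 per site per month. Randomization is at most 10 days before fraction 2, so swapping entries needs another eligible participant at the same site at the same time. Consent comes before eligibility is determined, a consented participant who is not randomized is documented as a screen failure (section 5.4), and the arm is released centrally. Steering every entry is therefore an upper bound.
- **Early stopping is a thin route.** The 3-fraction rule is the same in both arms, so steering likely dropouts mainly changes arm counts.
- **Larger blocks lower the average guess rate only modestly,** from about 72% to about 67%.

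A reader might also infer that the investigator who founded the manufacturer could exploit the pattern. The documents do not support this: section 11.4 says that he will not enroll patients, and no text links him to allocation.

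What remains is that the sizes are printed, some assignments can be known in advance, and the remedy costs almost nothing.

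**Conclusion.** The point holds as a minor design weakness. Allocation is about 72% guessable (70.8-75.0% for any mix of 2 and 4). About 10% of assignments are certain if the two sizes are equally likely. These figures assume that staff track their own site's assignments, which open-label conduct allows; the certainty figure also assumes that they know the sizes, which the protocol prints.

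Bias in the primary contrast is possible but probably small: 3.4% false non-inferiority instead of 2.5% at an assumed 0.05 SD with every entry steered. A reader might carry the same formula further and infer a rate of 10%, which it gives at 0.25 SD. The documents offer no basis for steering of that strength, and the crossover makes it unlikely. They do not show that the primary result is compromised.

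**What to change.** In section 10.2, delete the bracketed size range and state that allocation uses randomly varying even blocks within site, with the sizes held by the study statisticians in a restricted file and not disclosed to sites. Generate the unused list positions with blocks of 4, 6 and 8. If accrual has begun, complete the current block at each site first.

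Both parts are needed. Withholding sizes removes certainty but does not stop the running-count guess, and sites have already been able to read 2-4. New sizes cut certain assignments from about 10% to about 2% and correct guesses from about 72% to about 67% even if they leak. If they stay undisclosed, the gain in certainty is larger.

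A cap on imbalance (big stick, tolerance 3) is not the better choice here. It lowers average guessing further, but about 15% of assignments are then forced and known to anyone who has the rule.

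The cost is one sentence and a regenerated list in the existing system. A block of 8 allows an imbalance of up to 4 per site, against 2 now. An 18/22 split instead of 20/20 multiplies the SE by √(1/18 + 1/22)/√(2/20) = 1.005. The extreme of 4 at both sites in the same direction (16/24) gives √(1/16 + 1/24)/√(2/20) = 1.021.

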10.3 Evaluation of Sample Populations and Criteria

10.3.1 Study Population

Safety: All randomized participants receiving at any protocol treatment will be evaluated for safety outcomes.

Evaluable: All randomized eligible participants receiving at least 3 fractions of treatment will be evaluated for study outcomes.

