6 STUDY INTERVENTION

6.1 Description of Study Intervention(s)

Participants will be assigned to Arm A or Arm B, as described in section 4.1 and Figure 1. Fraction 1 for all participants (both Arms) will receiving standard of care packing. During fractions 2-5 of brachytherapy, participants will have vaginal packing alternating between the BrachyGel Vaginal Hydrogel Packing System and standard of care vaginal packing, strategy which will include gauze vaginal packing or rectal retractor.

For Arm A of the study, the BrachyGel Packing System will be used during fractions 3 and 5. Standard packing will be used for fractions 1, 2 and 4.

For Arm B of the study, the BrachyGel Packing System will be used during fractions 2 and 4. Standard packing will be used for fractions 1, 3 and 5.

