7.2 Participant Discontinuation/Withdrawal

Participants are free to withdraw from participation in the study at any time upon request.

A participant's study treatment would be discontinued for the following reasons:

- Pregnancy
- Significant study intervention non-compliance
- Severe, CTCAE Grade ≥ 4 adverse event considered at least possibly related to the packing procedure
- Participant is unable to receive further brachytherapy due to an adverse event or a change in status (e.g. decline due to disease, change in goals of care, development of metastases).
- Participant decision to withdraw from study treatment and/or the study

The reason for participant discontinuation or withdrawal from study treatment will be recorded on the case report form. Participants that withdraw from study treatment only, will continue with study follow-up. Participants that withdraw from study treatment and study follow-up will not be contacted for any further study visits.

Version Date: 11/16/2021

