10 STATISTICAL CONSIDERATIONS

10.1 Design

This is a two-center, stratified and randomized, four period, two arm crossover, noninferiority trial to demonstrate that BrachyGel Vaginal Hydrogel Packing System (hydrogel) is non-inferior to standard method vaginal packing (standard) in dose thresholds for D2cc (in Gy) for rectum and bladder by more than a non-inferiority margin of δ =1 Gy. Outcomes will be measured after each of 5 treatment fractions with results from the 1st fraction serving as the baseline measurement for each participant. D2cc measurements within organs varies between fractions as well as by participants, thus, each participant will receive both types of vaginal packing with order of packing type being chosen at random. Specifically, all participants will receive the standard method during the 1st fraction and then either sequence A (standard-hydrogel-standard-hydrogel) or sequence B (hydrogelstandard-hydrogel-standard) chosen at random, for the remaining four fractions. It is possible for participants to require less therapy during the final fraction (ie maximum therapy has been applied to the tumor), thus, the choice of ordering is limited to these two orderings to ensure that both packing types are administered to each participant with the primary assessment based upon fraction 2 and 3 data (ie, a two period, two treatment crossover).

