13 APPENDICES

13.1 Schedule of Activities (SoA)

| Procedures | Screening (within 6 weeks of Brachytherapy 1) | Brachytherapy 1 | Brachytherapy 2 | Brachytherapy 3 | Brachytherapy 4 | Brachytherapy 5 | 30 Day +/- 2 weeks Safety Follow-up |
|---|---|-----------------|-----------------------|-----------------|-----------------|-----------------|---|
| Informed consent | Х | | | | | | |
| Demographics | Х | | | | | | |
| Baseline conditions/assessment | X ² | | | | | | |
| Randomization | | | X ⁵ | | | | |
| Brachytherapy ¹ | | X^4 | Χ | Χ | Χ | Χ | |
| Physical exam | X ² | | | | | | X |
| Performance status | X ² | | | | | | X |
| Concomitant medications related to pain control during procedure ⁷ | | | Х | Х | Х | Х | |
| Physician Assessments of imaging/packing experience | | | Х | Х | Х | Х | |
| Physicist Assessments of imaging/packing experience | | X ⁶ | Х | Х | Х | Х | |
| Participant survey ³ | | | Х | Х | Х | Х | |
| Adverse event review and evaluation | | | X | | | X | Х |

Version Date: 11/16/2021

¹ Alternations will be based on Arm Assignment according to *Figure 1*.

² Must occur within 30 days of Brachytherapy 1. The assessments can be collected on the same day as Brachytherapy 1.

³ Participant survey should be completed without 1 hour following removal of packing after completion of brachytherapy. Not collected if participant was sedated.

⁴ Brachytherapy 1 is considered to be a part of the screening visit. Brachytherapy 2 is considered to be the "start of treatment." Brachytherapy 1 must occur within 14 days of registration.

⁵ No sooner than 10 days before Brachytherapy 2.

⁶ Only the dosimetry measurements need to be collected for Brachytherapy 1.

⁷ Not collected if participant was sedated.

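### The evaluable set rests on a fraction count that the plan defines in two conflicting ways, and either count discards collected data after randomisation

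*Combined protocol and SAP*

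**What the plan says.** Section 10.3.1 defines two populations. The safety set covers randomised participants who received any protocol treatment. Everything else uses the evaluable set: "All randomized eligible participants receiving at least 3 fractions of treatment will be evaluated for study outcomes". The definition does not name the fractions, say whether fraction 1 counts, or require any particular measurement. No all-randomised set for the dosimetry or rating outcomes and no missing-data method is given elsewhere.

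The primary endpoints need two specific fractions. Section 10.3.2 says: "Each endpoint is the difference between D2cc dosimetry measurements obtained during periods 1 and 2", which are fractions 2 and 3.

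The order of packing is in section 6.1: "For Arm A of the study, the BrachyGel Packing System will be used during fractions 3 and 5", and "For Arm B of the study, the BrachyGel Packing System will be used during fractions 2 and 4". Fraction 1 is standard packing for everyone.

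Two places bear on how fractions are counted. Section 10.1: "Outcomes will be measured after each of 5 treatment fractions with results from the 1st fraction serving as the baseline measurement". Footnote 4 of the Schedule of Activities: "Brachytherapy 1 is considered to be a part of the screening visit"; its next sentence places the start of treatment at fraction 2.

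**The concern.** Two statisticians working from this protocol could build different primary analysis sets, both defensible from the text. In a non-inferiority trial planned on 20 evaluable participants per arm, that should be settled before any data are seen.

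Membership is also decided after randomisation, by how far the participant got through treatment. Stopping is foreseeable. Section 7.2 lists inability to continue brachytherapy, participant withdrawal, and "Severe, CTCAE Grade ≥ 4 adverse event considered at least possibly related to the packing procedure". Section 2.2.5 says the device has not been used in living humans, so its tolerability is unknown. If stopping is related to the packing just experienced, the rule can remove informative observations that were already collected.

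**Working it through.** **Step 1: who is kept.** Inputs: packing order from 6.1, the primary data requirement from 10.3.2, and the two counts from 10.1 and footnote 4 of 13.1. The rows give the last brachytherapy fraction received.

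| Last fraction | BrachyGel uses, Arm A / Arm B | Both primary D2cc values due | Evaluable if fraction 1 counts | Evaluable if counted from fraction 2 |
|---|---|---|---|---|
| 2 | 0 / 1 | no | no | no |
| 3 | 1 / 1 | yes | yes | no |
| 4 | 1 / 2 | yes | yes | yes |
| 5 | 2 / 2 | yes | yes | yes |

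- *Fraction 1 counted.* The cut falls between fractions 2 and 3, where the primary endpoint needs it, so no complete pair is lost. Those who end after fraction 2 are removed from all non-safety analyses, although their fraction 2 dosimetry and ratings were due (8.2, 8.3, 13.1). A participant who stops right after her first BrachyGel use is dropped in Arm B (fraction 2) and kept in Arm A (fraction 3). The mirror image also holds: one who stops right after her first standard placement in the study periods is dropped in Arm A (fraction 2) and kept in Arm B (fraction 3).
- *Counted from fraction 2.* Fractions 2, 3 and 4 are required. Anyone who ends at fraction 3 is dropped in both arms with both primary values in hand. Stopping right after the first BrachyGel use now means exclusion in both arms, so the contrast above disappears.

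**Step 2: the implied loss.** Section 10.4 plans 20 evaluable per arm and about 57 accrued, with no loss rate. Back-solving: 57 − 40 = 17, and 17/57 = 29.8%. The amendment history (13.5) says enrolment went from 70 to 57 to fit the budget. With 70 the same sum gives 1 − 40/70 = 42.9%. The 30% is therefore not a forecast of stopping.

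**Step 3: direction, fraction 1 counted (assumed figures).** Take 28 per arm, discomfort categories scored 1 to 4, 2 per arm stopping right after their first BrachyGel use with a score of 4, and the other 26 averaging 2.

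- All data: (2 × 26 × 2 + 4 × 4)/56 = 120/56 = 2.143.
- After the exclusion, which drops only Arm B's two: 112/54 = 2.074.

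The BrachyGel mean improves by 0.07. If the stopping follows standard placements instead, the same sum lowers the standard mean by 0.07. The sign depends on which packing prompts stopping.

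**Step 4: power, counted from fraction 2 (assumed figures).** Inputs from 10.4: margin 1.68, true difference 0.12, SD 1.56, 20 per arm, one-sided 2.5% t-test. The non-centrality is (1.68 − 0.12)/(1.56 × √(2/20)) = 3.16 on 38 degrees of freedom, giving 86.9% power. The plan's 94% does not reproduce at this level; a one-sided 5% test gives 92.8%. That is a separate matter, and 86.9% serves here only as the base.

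Suppose 57 accrued yields exactly 20 complete pairs per arm and 5%, 10%, 15% or 20% of them lack fraction 4:

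| Lacking fraction 4 | Per arm | Power |
|---|---|---|
| 0% | 20 | 86.9% |
| 5% | 19 | 85.1% |
| 10% | 18 | 83.0% |
| 15% | 17 | 80.7% |
| 20% | 16 | 78.1% |

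**The case against.** The best defence is that the statistical section settles the count. Section 10.1 speaks of five treatment fractions including the first, and three fractions on that count is what a fraction 2 and 3 difference needs. Footnote 4 is a scheduling note that never mentions evaluability; the amendment history uses the same idea for registration timing and for when surveys start. This makes the 10.1 count the more natural one, but it does not remove the conflict. Footnote 4 is current text. It agrees with 6.4, which lets registration follow fraction 1, and with 9.1.5, which starts event recording after fraction 2. It also defines the term on which 10.3.1 relies.

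A second defence is that the fraction 2 exclusion is minor. It does not touch the primary endpoint, since a participant without fraction 3 has no difference on any complete-case definition. Adverse events stay in the safety set and in the monitoring of 10.5. She must also stop brachytherapy altogether: an Arm B participant who declines only further BrachyGel is due standard packing at fraction 3 anyway. All of this stands. It confines the harm under the 10.1 count to non-primary dosimetry and the exploratory ratings.

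A reader might infer that the rule both treats the arms differently after first BrachyGel use and discards complete primary pairs. The table in the working shows that each needs a different count. A reader might also infer that the rule favours BrachyGel. The mirror-image loss of standard placements in Arm A means the documents support no fixed direction.

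**Conclusion.** The definition is ambiguous, and neither reading is sound for every outcome it governs. Under the 10.1 count the primary set is intact, but fraction 2 data are lost from the all-period and exploratory analyses in a way that can be informative and arm-dependent. Under the footnote 4 count, complete primary pairs are discarded in both arms because of a later event. That works against the reason given in 10.1 for resting the primary on fractions 2 and 3, namely that treatment may be cut back by the final fraction.

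The size cannot be established. The 0.07 shift in discomfort and the fall in power to between 85.1% and 78.1% rest on assumed stopping rates. A reader might take the 17 non-evaluable participants as the number this rule will exclude. The documents do not support that, because they give neither a loss rate nor reasons for loss. The case for acting rests on the conflict in the text and on how little it costs to resolve.

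**What to change.** In 10.3.1, replace the fraction count with sets defined by data and keep the eligibility restriction:

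- **Primary analysis:** all randomised eligible participants with D2cc recorded at both fractions 2 and 3, whatever happens later.
- **All-period dosimetry, discomfort, imaging and use experience:** all randomised eligible participants with at least one assessment at fractions 2 to 5.

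In 10.6, state that the repeated-measures model accepts incomplete sequences, for example a likelihood-based mixed model. The present wording does not specify the model enough to ensure this.

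The first set settles primary membership whichever count was meant. The second keeps fraction 2 data in both arms. The cost is a change of wording before analysis, with no new data or patients. The downside is some incomplete sequences in the all-period models. The change does not create a primary difference for a participant who lacks fraction 3.
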